6.6 Blinding of IMP

This is an open label study with no requirement for blinding.

6.7 Destruction of IMP

Following IMP accountability and written permission from the Sponsor to destroy IMP, documentation of destruction must contain, at a minimum, the following:

- Identity, lot number, or subject number
- Quantity of IMP destroyed
- Date of destruction
- Method of destruction
- Name and signature of person or company responsible for destruction

7 Assessment of Safety

The methods for collecting safety data are described below. All personnel involved with the study must ensure they are familiar with the content of this section.

7.1 Adverse Events and Laboratory Abnormalities

7.1.1 Clinical Adverse Events

An *Adverse Event* is any untoward medical occurrence in a subject, which does not necessarily have to have a causal relationship with the administration of an IMP. An AE can therefore be any unfavorable and unintended sign, symptom or disease temporally associated with the use of the IMP, whether or not considered related to the medicinal product. Pre-existing conditions that worsen in severity during the course of the study are to be reported as AEs.

All AEs occurring during the clinical study will be reported on the AE page of the eCRF.

The Investigator will assess the severity, causality (relationship to IMP), and seriousness of each AE.

Severity: The severity of AEs will be graded according to the National Cancer Institute Common Terminology Criteria for Adverse Events (CTCAE), version 4.0 or higher. The CTCAE displays Grades 1 through 5 with unique clinical descriptions of severity for each AE based on the general guideline below. Detailed instructions on grading of events by MedDRA system organ class and lower level term are available online.

- **Grade 1:** Mild; asymptomatic or mild symptoms; clinical or diagnostic observations only; intervention not indicated.
- **Grade 2:** Moderate; minimal, local or noninvasive intervention indicated; limiting age-appropriate instrumental activities of daily life (e.g., preparing meals, shopping for groceries or clothes, using the telephone, managing money).
- **Grade 3:** Severe or medically significant but not immediately life-threatening; hospitalization or prolongation of hospitalization indicated; disabling; limiting self-care activities of daily life (e.g., bathing, dressing and undressing, feeding self, using the toilet, taking medications, and not bedridden).
- **Grade 4:** Life-threatening consequences; urgent intervention indicated.
- **Grade 5:** Death related to AE.

Note: Severity is distinct from seriousness. Thus, a Grade 4 AE is not by default an SAE. An AE will be reported as serious only if the Investigator judges the event to meet the definition of an SAE as provided below.

Page 38 of 76

Causality: AEs will be assessed as not related, unlikely related, possibly related, or related to IMP. Table 1 provides general guidance on the assessment of causality. For data reporting purposes, AEs assessed as not related or unlikely related will be reported as unrelated to IMP, and AEs assessed as possibly related or related will be reported as related to IMP. Assessment of causality should be based on the Investigator's medical judgment and the observed symptoms associated with the event.

Relationship to IMP	Criteria for Judgment
Related	Reasonable temporal relationship of the clinical event to IMP administration AND cannot be reasonably explained by other factors (such as the subject's clinical state, concomitant therapy, and / or other interventions).
Possibly Related	The temporal relationship of the clinical event to IMP administration makes causal relationship possible but not unlikely AND other drugs, therapeutic interventions or underlying conditions do not provide a sufficient explanation for the observed event.
Unlikely Related	The temporal relationship of the clinical event to IMP administration makes causal relationship unlikely but not impossible AND other drugs, therapeutic interventions or underlying conditions provide a plausible explanation for the observed event.
Not Related	Data are available to clearly identify an alternative cause for the reaction.

Table 1Assessment of Causality

Seriousness: AEs will be classified as serious or non-serious according to the definitions provided below.

A serious adverse event is any AE that is or leads to any of the following:

- Death
- Immediately life threatening (An AE is considered "life threatening" if, in the view of either the Investigator or Sponsor, its occurrence places the subject at immediate risk of death. It does not include an AE that, had it occurred in a more severe form, might have caused death)
- Requires inpatient hospitalization or prolongation of existing hospitalization
- Congenital anomaly/birth defect
- Persistent or significant disability or incapacity

Page 39 of 76

• An important medical event that may not result in death, be life threatening, or require hospitalization may be considered an SAE when, based upon appropriate medical judgment, the event may jeopardize the subject and may require medical or surgical intervention to prevent one of the outcomes listed above.

Planned hospitalizations to accommodate a study procedure are not considered an SAE. However, during the hospitalization, adverse events will be collected and assessed for seriousness & reported appropriately (i.e., Important medical event or prolonged hospitalization).

All AEs that do not meet any of the criteria for an SAE should be regarded as *non-serious adverse events*.

All SAEs and IARs must be reported to the Sponsor as described in Section 7.4.

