	 At Week 6 (and after at least 4 infusions in the extension study), subjects receiving a starting dose of 0.35 mg/kg qw or 1 mg/kg qw will have their dose changed to 1 mg/kg qow. Similarly, subjects who were receiving a starting dose of 3 mg/kg qw for the first 4 infusions will transition to the 3 mg/kg qow regimen. After Week 12, subjects receiving a dose of 1 mg/kg qow may have their dose increased to 3 mg/kg qow based on observed safety and tolerability and/or clinical response to treatment.
	 After Week 12, subjects receiving a dose of 3 mg/kg qow may be considered for a dose adjustment to 3 mg/kg qw based on observed safety and tolerability and/or clinical response to treatment.
	 In the event of poor tolerability at any time during the extension study, the dose may be reduced at the discretion of the Investigator. If a subject cannot tolerate the lowest starting dose (0.35 mg/kg qw) despite measures taken to manage any IARs, he/she will be discontinued from treatment.
Duration of IMP administration	The duration of each subject's treatment in the study will vary but is expected to be at least 26 weeks and approximately 5 years.
Reference therapy	No reference therapy will be administered in this study.
	Safety The primary safety endpoints will include the incidence of adverse events (AEs) SAEs, and IARs; changes in vital signs (blood pressure, heart rate, respiratory rate, and temperature), physical examination findings, 12-lead electrocardiogram (ECG) parameters, and clinical laboratory tests (CBC/hematology, serum chemistry and urinalysis); use of concomitant medications/therapies; and characterization of anti-sebelipase alfa anti-drug antibodies (ADAs), including ADA positive rate, time to ADA positivity, peak ADA titer, and time to peak ADA titer. The effect of ADAs on the safety of sebelipase alfa will also be explored. A further characterization of ADAs, including inhibitory ADAs, may be performed as a separate pooled analysis across studies, and will be reported separately from this protocol.

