7.4.3 Sponsor Reporting: Notifying Regulatory Authorities

The Sponsor is required to report certain study events in an expedited manner to the FDA, the European Medicines Agency, and to all country Regulatory Authorities where the study is being conducted. The following describes the safety reporting requirements by timeline for reporting and associated type of event:

Within 7 calendar days

Any study event that is:

associated with the use of the study drug, unexpected, fatal or life-threatening.

Within 15 calendar days

Any study event that is:

associated with the use of the study drug, unexpected, and serious, but not fatal or life-threatening.

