2.2 Study Endpoints

2.2.1 Safety Endpoints

This study is designed primarily to evaluate the safety and tolerability of long-term treatment with SBC-102, administered as weekly (qw) and biweekly (qow) IV infusions. The primary safety endpoints in this study will include:

- The incidence of:
 - Adverse events (AEs).
 - Serious adverse events (SAEs).
 - Infusion Associated reactions (IARs).
- Change/shift from baseline in:
 - Vital signs.
 - Physical examination findings.
 - Clinical laboratory tests.
 - 12-lead ECG parameters.
 - Use of concomitant medications/therapies.
- Characterization of anti-drug antibodies (ADAs) including:
 - Antibody positive rate.
 - Time to first antibody positive result.
 - Median and peak ADA titer.
 - Time to peak ADA titer.

A further characterization of ADAs, including neutralizing ADAs, may be performed as a separate pooled analysis across studies, and will be reported separately.

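### Protocol Section 7.1.1 defines an event that the Sponsor alone considers immediately life-threatening as an SAE, but reports an AE as serious only on the Investigator's judgment, so such an event could be left out of the SAE table

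*Protocol*

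**What the plan says.** Protocol Section 7.1.1 begins by giving three assessments to one person: "The Investigator will assess the severity, causality (relationship to IMP), and seriousness of each AE".

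Under severity, a note after the CTCAE grades separates grade from seriousness. It says "Thus, a Grade 4 AE is not by default an SAE", and continues: "An AE will be reported as serious only if the Investigator judges the event to meet the definition of an SAE as provided below".

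Under seriousness, the definition reads "A serious adverse event is any AE that is or leads to any of the following", followed by six criteria, any one of which is enough. The second is that the event is immediately life-threatening, which applies if, "in the view of either the Investigator or Sponsor, its occurrence places the subject at immediate risk of death". No other criterion names the Sponsor. The section ends by classing as non-serious only those AEs that satisfy none of the criteria.

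Protocol Section 7.3 has seriousness entered in the eCRF for every AE, without saying whose assessment it is when the two parties differ. SAP 5.3 has data analysed as they stand in the database. SAP 11.2.1 tabulates SAEs both as numbers of events and as numbers and percentages of subjects, again without saying whose classification is used.

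On the status of the endpoint, the protocol synopsis states "The primary safety endpoints will include the incidence of adverse events (AEs) SAEs, and IARs". SAP 2.2.1 opens its list with "The primary safety endpoints in this study will include" and includes SAE incidence in it.

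**The concern.** The definition and the reporting sentence stand in the same section but do not use the same decision-maker. The definition lets the Sponsor's view alone satisfy the life-threatening criterion. The reporting sentence makes the Investigator's judgment a necessary condition for calling any event serious. If the two parties disagree on immediate risk of death, the plan gives two classifications for one event and no rule for choosing between them.

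What is at stake is the content of the SAE table. This is an open-label safety study of at most 9 subjects, and one subject more or less with an SAE is visible in the results. Without a written rule, the choice would be made with the event already known. It could leave an event that meets the protocol's own definition out of the tabulation of a primary safety endpoint.

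**Working it through.** **Step 1. Set the two rules side by side.** Take an AE that meets none of the other five criteria, so that only the life-threatening one is in question.

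| Immediately life-threatening in the view of | By the definition | By the reporting sentence |
|---|---|---|
| Investigator and Sponsor | SAE | reported as serious |
| Investigator only | SAE | reported as serious |
| Sponsor only | SAE | not reported as serious |
| Neither | non-serious | not reported as serious |

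The rules differ in the third row only. If another criterion applies, such as hospitalization, the Sponsor's view on risk of death is not needed and this conflict does not arise.

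**Step 2. Look for a rule that settles the third row.** The CTCAE grade does not, because the note says that Grade 4 is not automatically serious. Protocol 7.3, SAP 5.3 and SAP 11.2.1 give no Sponsor upgrade and no way to resolve a disagreement. Read together, Protocol 7.1.1 (the Investigator assesses), Protocol 7.3 (the eCRF records) and SAP 5.3 (data are analysed as collected) imply that the Investigator's entry reaches the table. The third-row event would then be absent from it.

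**Step 3. Check that the case can occur.** Protocol 7.2.1 sends all infusion associated reactions to the Sponsor within 24 hours, whether serious or not. The Sponsor will therefore see events that the Investigator has called non-serious.

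**Step 4. Size.** The plan states no figure on this point, so there is none to reproduce. Inputs for an illustration:

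- n = 9, the maximum enrolment (Protocol 4.2).
- Exact binomial 95% intervals, the method named in Protocol 8.1 and SAP 5.1.
- x = 0 or 1 subjects with an SAE. This assumes one third-row event, in a subject with no other SAE, and no SAE in anyone else.

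The lower limit is the 0.025 quantile of Beta(x, n − x + 1), set to 0 when x = 0. The upper limit is the 0.975 quantile of Beta(x + 1, n − x).

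- Reporting sentence followed: 0/9 = 0%. Upper limit = 1 − 0.025^(1/9) = 33.6%. Interval 0 to 33.6%.
- Definition followed: 1/9 = 11.1%. Lower limit = 1 − 0.975^(1/9) = 0.3%. Upper limit = 0.975 quantile of Beta(2, 8) = 48.2%. Interval 0.3 to 48.2%.

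If fewer subjects are treated (assumed range 6 to 8), one subject is worth 1/8 = 12.5 to 1/6 = 16.7 percentage points.

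SAP 11.2 counts a subject once within each preferred term and system organ class, and SAP 11.2.1 reports percentages of subjects. If the affected subject already has another SAE, the overall percentage of subjects with any SAE does not move. Only the number of events rises, by one.

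**The case against.** The strongest defence is that the sentences can be read together. The reporting sentence closes a note whose purpose is to stop a CTCAE grade from deciding seriousness. It sends the Investigator to the definition, and the definition already contains the Sponsor's view. On this reading the Investigator applies a criterion that the Sponsor's opinion can satisfy. That is a fair account of what may have been intended, but it does not dispose of the words "An AE will be reported as serious only if the Investigator judges the event to meet the definition of an SAE as provided below". They make the Investigator's judgment a necessary condition, and nothing obliges the Investigator to adopt the Sponsor's view.

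A second defence is that the documents do imply whose entry is analysed: the Investigator's, through the eCRF. This is correct, but it means that the table follows the reporting sentence and not the definition, which is the problem.

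A third is that the case is narrow. This stands. One criterion of six is affected. The parties must disagree, and no other criterion may apply, including the one for important medical events, which rests on medical judgment. The tables are descriptive and no formal hypothesis test is planned (Protocol 8.10.1).

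A reader might also infer more than the documents support:

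- *That a 7-day expedited report could be missed.* Section 7.4.3 places that duty on the Sponsor for any event "associated with the use of the study drug, unexpected, fatal or life-threatening". It does not depend on the Investigator's seriousness judgment.
- *That subject protection fails downstream.* Home infusion needs approval from both Investigator and Sponsor (6.1.3), the Safety Committee reviews aggregate safety data and emerging signals (7.5.1), and the Sponsor may suspend dosing for potential safety risks (7.6).
- *That disagreement is most likely for the gravest events.* The Grade 4 remark separates grade from seriousness. It says nothing about how often the two parties would differ.
- *That every reclassified event moves incidence by at least 11.1 points.* This holds only when the subject has no other SAE.

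**Conclusion.** The inconsistency is real and lies within one section. An event that the Sponsor alone considers immediately life-threatening, and that meets no other criterion, is an SAE under the definition. Under the reporting sentence it would not be reported as serious, and so would not enter the SAE table for a primary safety endpoint.

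The effect is confined to classification and tabulation. It does not touch sample size, error rates or expedited reporting. In the illustrative case it is the difference between 0% and 11.1% of 9 subjects, with wide and overlapping intervals. Otherwise it is one event in the event count. The illustration rests on full enrolment and a single such event. The probability of that event cannot be estimated from the documents. The point should be corrected because the text contradicts itself on a primary endpoint and the correction is small, not because a large bias has been shown.

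**What to change.** In the note under severity in Protocol Section 7.1.1, replace the reporting sentence with one that agrees with the definition, for example: *An AE will be reported as serious if it meets the definition of an SAE below, including when the Sponsor alone considers it immediately life-threatening.*

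In SAP 11.2.1, add that such events are counted as SAEs, and that the SAE listing shows whether the classification came from the Investigator or the Sponsor.

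The change need go no further than the life-threatening criterion, the only one for which the protocol gives the Sponsor a view. Letting the Sponsor upgrade on any criterion, or barring it from downgrading, would be a new policy that the present text does not call for.

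The cost is one sentence in each document and one data flag for the source of the classification. The SAE count may be slightly higher.

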7.1.2 Laboratory Test Abnormality

Laboratory test results will be recorded, or provided on the laboratory reports submitted directly from the central laboratory. Out of range laboratory test values should not be reported as AEs UNLESS they are considered to be a clinically significant abnormality by the Investigator.

7.1.3 Infusion Associated Reactions

Infusion-associated reactions will be considered AEs of special interest. Any AE that occurs during the infusion or within 4 hours after the infusion and is assessed by the Investigator as at least possibly related to IMP will be designated as an IAR. In addition, if, at any time during the study, the Investigator observes symptoms that he/she considers to be consistent with an IAR or a hypersensitivity reaction related to the administration of IMP, the symptoms will be recorded as an AE(s) and designated as an IAR(s).

As with any ERT, medications and equipment for the treatment of hypersensitivity reactions must be available for immediate use in case of unexpected severe hypersensitivity reactions. These supplies include, but are not restricted to, oxygen, acetaminophen, antihistamines (e.g. diphenhydramine, parenteral and oral [PO]), corticosteroids, epinephrine, and cardiopulmonary resuscitation devices.

General guidelines for classifying the severity of a reaction are provided below, and examples of mild, moderate, and severe IARs are provided in Appendix F.

For similar biological products, most acute IARs occur within 2 hours of the infusion. Signs of a possible acute IAR may include:

• Hyperemia, flushing, fever and/or chills, nausea, pruritus, urticaria, gastro-intestinal symptoms (vomiting, diarrhea, abdominal cramping), cardiopulmonary reactions, including chest pain, dyspnea, wheezing, stridor, hypotension or hypertension.

Page 40 of 76

If any of the above signs and symptoms are observed during the infusion and the subject does not show any respiratory symptoms and remains hemodynamically stable:

- a) The infusion rate must be slowed (reduced to half the rate being given at the onset of the event, e.g. from 125 mL/hr to 62.5 mL/hr) and the infusion time extended. Once the event has resolved, the infusion should continue for a minimum of 30 minutes at the reduced rate before the rate is increased to 75% of the original rate on the infusion schedule.
- b) In accordance with institutional standard of care for the subject's age, treatment with an antihistamine should be considered.

In subjects who experience severe infusion reactions with clinically significant cardiovascular effects (hypotension defined as a decline approaching 20-30% of their pre-infusion value), respiratory effects (significant shortness of breath, stridor, laryngeal edema or swelling of tongue), or other effects:

- a) The infusion should be discontinued.
- b) The subject should be treated for an anaphylactic reaction with intravenous antihistamines, corticosteroids, and epinephrine, if necessary in accordance with institutional standard of care for the subject's age.
- c) Dosing of the patient will be suspended until the Safety Committee has completed review of the IAR, and any other relevant safety data.
- d) Subjects who experience a moderate or severe IAR should have a serum sample collected for tryptase 1 to 3 hours after the IAR onset and another serum sample for tryptase and ADA at least 4 days after the IAR. Skin testing may be considered.

Additional details on the management of subjects with IARs are provided in Appendix F.

7.2 Handling of Safety Parameters

7.2.1 Serious Adverse Events (Immediately Reportable to the Sponsor)

All SAEs and IARs (serious and nonserious), must be reported to the Sponsor or designee immediately and no later than 24 hours after the Investigator's first knowledge of the event (expedited reporting).

The definition and reporting requirements are in accordance with ICH Guidance for Clinical Safety Data Management, Definitions and Standards for Expedited Reporting (Topic E2, 1995).

7.2.2 Adverse Event Reporting Period

The study period during which AEs must be reported is defined as the period from the signature of written consent to the end of the study treatment follow-up. For this study, AEs will be reported from the date of written informed consent until completion of the follow-up visit at approximately 30 days after the last dose of IMP. If a subject experiences an SAE that is considered to be related to study treatment at any time after the study, it must be reported to the Sponsor.

Page 41 of 76

7.2.3 Treatment and Follow-up of Adverse Events

Treatment of AEs is at the discretion of the Investigator and should follow the standards of medical care at the Investigator's institution.

All AEs and SAEs will be followed until resolution, the condition stabilizes, or the Investigator and Sponsor agree that follow up is no longer necessary. SAEs that are ongoing after completion of the last scheduled visit should continue to be followed up to determine the final outcome. Non-serious AEs that are ongoing after completion of the last scheduled visit should be followed up until the event resolves or stabilizes, or for a minimum of 30 days after the last dose of IMP (whichever occurs first). Rules for AE/SAE follow-up apply to all subjects, including those withdrawn prematurely, to the extent allowed by the subject's consent.

The Investigator will ensure that AE/SAE follow-up includes further investigations consistent with appropriate medical management and subject consent to elucidate the nature and/or causality of the AE/SAE.

